## **8. RESEARCH QUESTION AND OBJECTIVES**

The primary objective of this exploratory meta-analysis is to evaluate the frequencies, incidence rates, and hazard ratios of lower-limb amputation (LLA) events (primary outcome) and of AEs related to amputation (secondary outcome) in patients treated with empagliflozin compared with placebo in the pooled population of the long-term studies 1245.25, 1245.110, and 1245.121 (SAF-M1), in the pooled population of studies 1245.110 and 1245.121 (SAF-M2), and in each of the 3 studies separately.

The exploratory objectives are to evaluate the frequencies of recurrent LLA events and of AEs related to recurrent LLA events and to assess the frequencies and incidence rates of patients with AEs related to amputation preceding the amputation for empagliflozin compared with placebo in SAF-M1, SAF-M2, and in each of the 3 studies separately. Further exploratory objectives are to evaluate the frequencies, incidence rates, and hazard ratios of the primary and secondary outcomes by subgroup and of the secondary outcome by grouped PTs for SAF-M1 and SAF-M2 as well as to assess details on LLA events for SAF-M2 in patients treated with empagliflozin compared with placebo.

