Disposition, demographics, exposure	Yes	Yes	Yes	Yes	Yes
Concomitant diagnoses and therapies	Yes	Yes	Yes	Yes	Yes
Lower limb amputation					
Frequencies	Yes	Yes	Yes	Yes	Yes
Incidence rates	Yes	Yes	Yes	Yes	Yes
Time to onset analyses	Yes	Yes	Yes	Yes	Yes
Time to onset analyses with competing risk	Yes	-	-	-	-
Sensitivity analyses (heterogeneity analyses, forest plot)	Yes	Yes	-	-	-
Adverse events related to amputations (definition based on list of PTs)					
All patients					
Frequencies	Yes	Yes	Yes	Yes	Yes
Incidence rates	Yes	Yes	Yes	Yes	Yes
Time to onset analyses	Yes	Yes	Yes	Yes	Yes
Patients with amputations only, i.e. preceding events					
Frequencies	Yes	Yes	Yes	Yes	Yes
Incidence rates	Yes	Yes	Yes	Yes	Yes
Time to onset analyses (KM only)	Yes	Yes	Yes	Yes	Yes
Lower limb amputation events occurring after the first LLA event					
Descriptive Statistics (Frequency tables with absolute and relative frequencies)	Yes	Yes	Yes	Yes	Yes
Adverse Events related to amputations occurring after the first LLA event					
Descriptive Statistics (Frequency tables with absolute and relative frequencies)	Yes	Yes	Yes	Yes	Yes

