##### *AEs related to amputation*

Subgroup analyses for SAF-M1 and SAF-M2 will be carried out.

For AEs related to amputation, analyses for different grouped events will be performed (see the SAP [[c16853237](#), Appendix 6.1]). Cumulative proportions of patients and the number of patients at risk will be provided. In addition, Cox regression analyses will be performed for vascular AEs, diabetic-foot-related AEs, wound/infection, nervous system disorders, and

volume depletion events if the sample size is statistically sufficient, i.e. at least 14 patients with events in total over the 2 treatment groups have been reported.

An ITT approach will be used as a secondary analysis, which includes all events during the observation period after starting randomised treatment, regardless if the patient was taking study medication or not when the event occurred.

A listing of AEs with onset during any treatment other than the randomised treatment will be provided.

Additionally, AEs related to amputation preceding the amputation will be summarised for patients with amputation; AEs with onset after the amputation will not be considered in the analysis of this sub-population.

AEs related to amputations occurring after the first amputation event will be summarised using descriptive statistics (frequency tables with absolute and relative frequencies).

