4.3.2.2.2 Adverse events related to amputation

The types of analyses to be performed on these events are outlined in [Table 4.3:1](#). The analyses will be performed for these events based on all treated patients and in the subgroup of patients with a subsequent amputation, but for events before the actual amputation only. Events occurring after the first amputation will not be included.

Frequency tables of patients with events preceding amputations (see [Section 4.1.1.2](#)) by treatment, group of PT as specified in Appendix 6.1, SOC and PT will be provided. In addition incidence rates will be displayed.

Kaplan Meier analyses (cumulative incidence functions) for time to first event will be provided by treatment and stratified by study; hereby the analysis will not be provided on individual PT level but events being grouped into vascular AEs, diabetic foot related AEs, wound/infections or nervous system disorders and volume depletion (see [Appendix 6.1](#)). Cumulative proportion of patients and the number of patients "at risk" will be provided. In addition, Cox regression analyses will be performed for the above defined AE groups if sample size is statistically sufficient, i.e. if at least 14 patients with events in total over the 2 treatment groups have been reported.

A listing of AEs with onset during any other than randomized treatment will be provided.

AEs related to amputations occurring after the first amputation event will be analysed using descriptive statistics and will be provided in the final report.

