6 APPENDIX

6.1 LIST OF PREFERRED TERMS FOR PRECEDING/RELATED EVENTS

Vascular AEs

Angiopathy

Arterial bypass operation

Arterial disorder

Arterial graft

Arterial occlusive disease

Arterial stenosis

Arterial stent insertion

Arteriosclerosis

Arterial thrombosis

Arterial therapeutic procedure

Diabetic microangiopathy

Diabetic vascular disorder

Femoral artery occlusion

Iliac artery occlusion

Intermittent claudication

Ischaemic limb pain

Microangiopathy

PAOD Peripheral arterial occlusive disease

Peripheral ischaemia

Peripheral coldness

Peripheral artery stenosis

Peripheral artery restenosis
Peripheral artery occlusion
Peripheral artery thrombosis
Peripheral vascular disorder
Peripheral ischaemia
Peripheral arterial re-occlusion
Peripheral vascular disorder
Poor peripheral circulation
Peripheral artery angioplasty
Peripheral endarterectomy
Peripheral artery bypass
Peripheral artery stent insertion
Spontaneous amputation
Thrombosis

Diabetic foot related AEs

Atherosclerotic gangrene

Bone abscess

Diabetic foot

Diabetic foot infection

Diabetic gangrene

Diabetic neuropathic ulcer

Diabetic ulcer

Dry gangrene

Cellulitis enterococcal

Cellulitis staphylococcal

Cellulitis streptococcal

Cellulitis gangrenous

Extremity necrosis

Gangrene

Infections Cellulitis

Infected skin ulcer

Infected skin ulcer

Ischaemic ulcer

Localised infection

Necrosis ischaemic

Neuropathic ulcer

Osteitis

Osteomyelitis

Osteomyelitis acute

Osteomyelitis bacterial
Osteomyelitis chronic
Osteomyelitis fungal
Osteomyelitis salmonella
Osteonecrosis
Penetrating atherosclerotic ulcer
Post-operative wound infection
Skin erosion
Skin ulcer
Staphylococcal osteomyelitis
Soft tissue infection
Subperiosteal abscess

Wound/Infection

Abscess limb

Burn infection

Impaired healing

Wound

Skin wound

Skin infection

Subcutaneous abscess

Vasculitic ulcer

Wound abscess

Wound complication

Wound dehiscence

Wound infection

Wound infection bacterial

Wound infection fungal

Wound infection staphylococcal

Wound infection pseudomonas

Wound necrosis

Wound sepsis

Wound treatment

Nervous System Disorders

Areflexia

Autonomic neuropathy

Burning sensation

Diabetic neuropathy

Hypoesthesia

Neuropathy peripheral

Paraesthesia

Peripheral sensory neuropathy

Peripheral sensorimotor neuropathy

Sensory disturbance

Volume depletion

Hypovolaemia

Dehydration

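### The only table serving the objective on AEs related to recurrent amputation takes any listed AE after the first amputation, whether or not another amputation occurs

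*Protocol*

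**What the plan says.** Protocol section 8, repeated on the title page and in the abstract, states: "The exploratory objectives are to evaluate the frequencies of recurrent LLA events and of AEs related to recurrent LLA events".

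Three places describe the analysis that corresponds to the AE half of that objective:

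- Protocol section 9.7.2.1: "AEs related to amputations occurring after the first amputation event will be summarised using descriptive statistics".
- Protocol Table 9.7: 2, with a matching row in SAP Table 4.3: 1: "Adverse Events related to amputations occurring after the first LLA event". The output is a descriptive frequency table for both pools and each study.
- SAP section 4.3.2.2.2: "AEs related to amputations occurring after the first amputation event will be analysed using descriptive statistics and will be provided in the final report".

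Protocol section 9.3.2.2 and SAP section 4.1.2 define AEs related to amputation through the preferred terms in SAP Appendix 6.1. Both say that such events need not lead to an amputation. The list includes "Post-operative wound infection" and "Wound dehiscence", as well as wound complication, wound necrosis and impaired healing.

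**The concern.** The objective asks about AEs tied to a recurrence. The table asks only whether a listed AE followed a first amputation. Several listed terms can describe poor healing of the first amputation wound, so a patient with one toe amputation, a dehisced wound and no further amputation qualifies. A reader who takes the table as the answer to the objective cannot tell such patients from those whose listed AE came before a second amputation.

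What is at stake is one exploratory, descriptive result. No hazard ratio, test or decision rule depends on it.

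**Working it through.** The documents state no figure on this point, so the check sets the texts side by side.

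1. **Population wanted by the objective.** Patients with a recurrent LLA, meaning at least two LLAs, and a listed AE related to the recurrence.

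2. **Population counted by the plan.** Patients with at least one LLA and any Appendix 6.1 term with onset after the first. Neither document adds a condition that a second LLA occurred, that the AE began before it, or that the AE was recorded as leading to it. The counting unit is the patient, not the AE (protocol section 9.7.2.2, SAP section 4.3.2.2).

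3. **Relation between the two.** Every patient in step 1 whose listed AE began after the first LLA is also in step 2. Step 2 adds patients with one LLA and a later listed AE, and patients with two or more LLAs whose listed AEs all came after the last. The planned count can therefore equal or exceed the wanted one, never fall below it.

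4. **Whether another output closes the gap.** The analysis of AEs preceding amputation leaves out events after the first amputation (protocol section 9.7.2.1, SAP section 4.3.2.2.2), so the interval between a first and a second LLA is not covered there. The table of LLA episodes per patient, the listing of patients with recurrent events and the summary of LLAs after the first (protocol section 9.7.2.1, SAP section 4.3.2.2.1) identify who had a recurrence. They do not divide the AE table.

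5. **Size of the excess.** The documents give neither a recurrence proportion nor a rate of listed AEs after an LLA. Purely assumed inputs show how little can be said. Take 100 patients with an LLA, and let 80% of those with a recurrence have a listed AE in between.
   - With 25% recurrence, 25 × 0.80 = 20 such patients. If 10%, 30% or 50% of the 75 single-LLA patients have a later listed AE, that adds 7.5, 22.5 or 37.5 patients. The single-LLA share of the table is 7.5/27.5 = 27%, 22.5/42.5 = 53% or 37.5/57.5 = 65%.
   - With 50% recurrence and 10%, the share is 50 × 0.10 = 5, and 5/(40 + 5) = 11%.

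   The result follows the assumptions, so none of these figures is an estimate for this study.

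**The case against.** The strongest reply is grammatical. The planned sentence can be read as AEs related to those amputations that come after the first, which would match the objective. Against this, the overview table uses the same phrase, AEs related to amputations, for the term defined by the preferred-term list, and neither document gives a rule that links an AE to a later LLA. If that reading was meant, the linkage rule is missing and the text still needs completing.

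Second, a reader might infer that wound complications of a single amputation will be reported as recurrence-related. The documents do not say so. The row is labelled as events after the first LLA, which correctly describes what is counted. The mismatch arises only because no other analysis serves the AE half of the objective.

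Third, a reader might infer that an arm with more first amputations would be shown unfairly. That is a denominator question, and it would apply equally to a table limited to recurrences: with the same recurrence proportion, more first LLAs give more second ones. The general rule bases percentages on the respective patient set, and the plan does not name patients with an LLA as that set for this row.

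Finally, wound infection or necrosis may itself precede a re-amputation, and SAP section 4.1.2 describes the listed events as often preceding amputation. These terms should therefore be separated by timing, not removed as surgical noise.

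**Conclusion.** The mismatch holds. Followed as written, the plan does not isolate AEs related to recurrent LLA, because patients with a single LLA and a later listed AE share the table with patients who had a recurrence. The direction follows from the definitions. The size cannot be computed from the documents.

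It would go too far to say that the whole objective goes unanswered. Its first half, the frequency of recurrent LLA, has its own table, listing and summary. The primary and secondary outcomes are not touched. The point merits a correction because the planned output does not deliver a quantity the protocol says it will evaluate. The conclusion rests on reading AEs related to amputation as the term defined by the preferred-term list, which is how both documents use it.

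**What to change.** Keep the planned table and split it by LLA dates, which are collected in 1245.110 and 1245.121 and were derived for 1245.25:

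- **(a)** patients with a second or later LLA and a listed AE with onset after the first LLA and on or before a later LLA;
- **(b)** patients with a second or later LLA whose listed AEs occur only after their last LLA;
- **(c)** patients with one LLA only and a listed AE after it.

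The rows do not overlap and add up to the planned count, so no planned information is lost. Give relative frequencies with patients with at least one LLA as the denominator and, for (a) and (b), also with patients with at least two. State how two amputations on the same date are treated, since each is to be reported separately. Add a note that row (a) shows timing only and may still include healing complications of the first LLA.

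Make the change in protocol Table 9.7: 2 and section 9.7.2.1, and in SAP Table 4.3: 1 and section 4.3.2.2.2. The cost is a few lines of text and one derived flag. The downside is small counts in rows (a) and (b). Rewording the objective to AEs after the first LLA would also make the documents consistent, but it would give up the question about recurrence.

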#### *Details on LLA events*

For SAF-M2, where additional information on LLA events are collected on the eCRF, the following analyses will be performed:

- Frequencies of reasons leading to the LLA
- Number of LLA episodes per patient
- Number of LLA episodes per patient excluding those due to trauma and tumor
- Level of amputation for the first LLA, excluding amputation due to trauma and tumor (highest)
- Number of patients having a major LLA as first LLA
- Number of patients with any major LLA
- Number of patients having a knee or above knee LLA as first LLA
- Number of patients with any knee or above knee LLA

#### 9.7.2.2 Analysis of AEs

AEs will be coded using the most recent version of the MedDRA coding dictionary. All analyses of AEs will be based on the number of patients with AEs (not the number of AEs). For this purpose, AE data will be combined in a 2-step procedure into AE records. In a first step, AE occurrences, i.e. AE entries on the CRF, will be collapsed into AE episodes provided that all of the following applies:

- The same MedDRA lowest level term was reported for the occurrences
- The occurrences were time-overlapping or time-adjacent (time-adjacency of 2 occurrences is given if the second occurrence started on the same day or on the day after the end of the first occurrence)
- Treatment did not change between the onset of the occurrences or treatment changed between the onset of the occurrences, but no deterioration was observed for the later occurrence

In a second step, AE episodes will be condensed into AE records provided that the episodes were reported with the same term on the respective MedDRA level and that the episodes are assigned to the same treatment. Internal BI guidelines will be followed for the handling of AE data. Frequency tables of patients with AEs by system organ class and preferred terms will be provided and sorted by frequency (within system organ class).

The primary analysis for AEs, the “on-treatment” approach, will be based on the concept of treatment-emergent AEs. That means all AEs with an onset date between first drug intake (post run-in) until 7 days after last drug intake (or time to last follow-up for analyses up to last follow-up) will be assigned to the randomised study drug (1245.25) or first study drug taken (1245.110, 1245.121).

An ITT approach will be used as a secondary analysis. All AEs with an onset date between first drug intake (post run-in) until time to last follow-up will be assigned to the randomised study drug (1245.25) or first study drug taken (1245.110, 1245.121).

#### 9.7.2.3 Subgroup analysis

All subgroup variables with categories are shown in [Table 9.3.3: 2](#). Subgroup analyses for SAF-M1 and SAF-M2 will be provided for frequency and incidence rate tables, KM analyses, and for Cox models. Subgroup analyses will be performed for LLA events and AEs related to amputation.

For Cox models for time to first event analysis, the following factors will be included in the model: study, treatment, <subgroup>, treatment-by-<subgroup> interaction.

For time-to-event endpoints, at a minimum, a count of events will be provided, and if sample size is statistically sufficient, i.e. 14 patients with events in total over the 2 treatment groups for each subgroup category, a statistical analysis using the Cox regression model will be performed. If the affected category is too small (<14 patients with events), the category may be only described descriptively and no inferential analysis is performed, or the category may be pooled with another category if this is justifiable from a scientific perspective.

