**1245.110 (EMPEROR-Preserved) and 1245.121 (EMPEROR-Reduced), both ongoing**

**Aim:** To investigate the safety and efficacy of empagliflozin versus placebo on top of guideline-directed medical therapy in patients with heart failure with reduced or preserved ejection fraction

**Population:** T2D and non-T2D, age ≥18 years, chronic HF (NYHA II–IV)

Figure 9.1: 1 Design of studies 1245.25, 1245.110, and 1245.121

QD/qd, once daily; T2DM, type 2 diabetes mellitus; LVEF, left ventricular ejection fraction; SoC, standard of care

\* Guideline-directed therapies

This meta-analysis will be exploratory. All analyses will be based on the treated set, which includes all patients treated with at least 1 dose of study medication (as randomised). Due to the different patient eligibility criteria (see [Section 9.2.2](#)) and methods in capturing LLA and related events (see [Section 9.3.2.1](#)), two analysis groupings will be used in the meta-analysis. SAF-M1 includes all 3 studies while SAF-M2 includes studies 1245.110 and 1245.121. All

analyses will be carried out separately for each SAF and for each study, unless otherwise indicated in [Section 9.7.1](#) and [9.7.2](#).

The primary outcomes are LLA events (see [Section 9.3.2.1](#)).

LLA events will be analysed using frequency analyses, incidence rates, Kaplan-Meier estimates, and Cox proportional hazards models to compare empagliflozin with placebo. For SAF-M2, where additional information on LLA events are collected on the eCRF, the reasons leading to LLA, the number of LLA episodes, level of LLA, etc., will be summarised.

As the primary analysis, the “on-treatment” approach will include events with an onset date within the treatment period (from first to last dose of study medication plus 7 days to account for the residual drug effect). An ITT approach will be used as a secondary analysis, which includes all events during the observation period after starting randomised treatment, regardless if the patient was taking study medication or not when the event occurred.

Since deaths are competing events to amputations, a competing risk analysis considering all-cause death and a cumulative incidence analysis will be carried out.

Subgroups by demographics, baseline medical conditions, and baseline therapies will be analysed for LLA events for SAF-M1 and SAF-M2 (see [Section 9.3.3](#) for subgroup variables).

The secondary outcomes are AEs related to amputation (see [Section 9.3.2.2](#)).

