## **9.2.2 Study population**

### **9.2.2.1 Study 1245.25**

Study 1245.25 included patients with type 2 diabetes mellitus and increased cardiovascular risk. Detailed eligibility criteria can be found in CTR 1245.25 [[c02695839](#), Section 9.3] and the key criteria are summarised below.

The key inclusion criteria were:

- Age  $\geq 18$  years, diagnosis of T2DM
- Drug-naïve or pretreated with any background therapy
- HbA1c criteria
  - Patients who were drug-naïve: HbA1c of 7 to 10%
  - Patients with background therapy: HbA1c of 7 to 9%
- BMI  $\leq 45$  kg/m^2
- With high cardiovascular risk, defined as  $\geq 1$  of the following criteria
  - History of myocardial infarction (>2 months prior to enrollment)
  - Multi-vessel coronary artery disease:  $\geq 2$  major vessels or left main coronary artery
  - Single-vessel coronary artery disease with no scheduled revascularization/Previously unsuccessful revascularization
  - Hospital discharge due to unstable angina pectoris (>2 months prior to enrollment)
  - History of stroke (>2 months prior to enrollment)
  - Peripheral occlusive arterial disease

The key exclusion criteria were:

- Uncontrolled hyperglycemia: fasting plasma glucose  $>240$  mg/dl
- Severe renal impairment defined as eGFR  $<30$  ml/min by MDRD formula
- Intake of an investigational drug in another trial within 30 days prior to intake of study medication in this trial, or participating in another trial (involving an investigational drug and/or follow-up)

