### **9.2.2.2 Studies 1245.110 and 1245.121**

Study 1245.110 will include patients with chronic heart failure with preserved ejection fraction. Study 1245.121 will include patients with chronic heart failure with reduced ejection fraction. Detailed eligibility criteria can be found in CTPs [[c03946327](#), [c09098452](#), Section 3.3] and the key criteria are summarised below.

The key inclusion criteria are:

- Age  $\geq 18$  years (Japan, age  $\geq 20$  years)
- Chronic HF NYHA class II to IV
- Ejection fraction (EF) and NT-proBNP criteria

- 1245.110: preserved EF (LVEF >40%) and elevated NT-proBNP (>300 pg/ml; >900 pg/ml for patients with atrial fibrillation)
- 1245.121: reduced EF (LVEF ≤40%) and elevated NT-proBNP (≥2500 pg/ml if EF 36 to 40%, ≥1000 pg/ml if EF 31 to 35%, ≥600 pg/ml if EF ≤30% or if EF ≤40% with documented hospitalisation for HF within 12 months prior to screening; for patients with atrial fibrillation, double the level of NT-proBNP is applied for each EF category)
- 1245.110 only: structural heart disease within 6 months or documented hospitalisation for HF within 12 months prior to screening
- 1245.121 only: stable dose of medical therapy for HF consistent with local and international cardiology guidelines

The key exclusion criteria are:

- Myocardial infarction, coronary artery bypass graft surgery or other major cardiovascular surgery, stroke or transient ischaemic attack ≤90 days before screening
- Heart transplant recipient, or listed for heart transplant
- Acute decompensated HF
- SBP ≥180 mmHg at randomisation
- Symptomatic hypotension and/or SBP <100 mmHg at screening or randomisation
- Impaired renal function defined as eGFR (CKD-EPI)cr <20 ml/min/1.73 m^2 or requiring dialysis at screening

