4.3.2.3 Subgroup analyses

Subgroup analyses will be performed for the subgroups displayed in [Table 4.3: 3](#). Subgroup analyses for SAF-M1 and SAF-M2 will be provided for frequency and incidence rate tables, KM analyses and for Cox models. Subgroup analyses will be performed for amputation events as well as for the adverse events related to amputations analysis.

For Cox models for time to first event analysis the following factors will be included in the model: study, treatment, <subgroup>, treatment by <subgroup> interaction.

For time-to-event endpoints, at a minimum, a count of events will be provided, and if sample size is statistically sufficient, i.e. 14 patients with events in total over the 2 treatment groups for each subgroup category, a statistical analysis using the Cox regression model will be performed. If otherwise the affected category is too small (<14 patients with events) a category may be only described descriptively and no inferential analysis is performed, or the category might be pooled with another category if this is justifiable from a scientific perspective.

Table 4.3: 3 Subgroup analyses

Variable	Subgroup Analysis Categories
Sex	Male Female
Race	White Black/African Asian Other
Geographical region	Europe Africa/Middle East North America Latin America Asia Other (if any)
Age (years) categories	Version 1 < 65 65 to < 75 75 to < 85 ≥ 85 or

	< 65
	65 to < 75
	= 75
	In case of low number of events for patients >= 85
Renal function (eGFR) (CKD-Epi) (mL/min/1.73m ²)	<30 30 to < 45 45 to <60 60 to <90 ≥90
Insulin use	Yes/No (Diabetic patients only)
Metformin use	Yes/No (Diabetic patients only)
SU use	Yes/No (Diabetic patients only)
Loop diuretics	Yes/No
Baseline HbA _{1c} (%)	<8.0, >=8.0
Baseline HbA _{1c} (%)	<8.5, >=8.5
Anticoagulant use	Yes/No
Anti-platelet use	Yes/No
Diuretics	Yes/No
Hypertension	Yes/No
Diabetes	T1DM T2DM No Diabetes (Diabetes yes/no if number of events to low)
Peripheral arterial occlusive disease	Yes/No
Diabetic foot at baseline	Yes/No (Diabetic patients only)
Coronary artery disease	Yes/No
Diabetic neuropathy	Yes/No
Diabetic retinopathy	Yes/No (Diabetic patients only)
History of lower limb amputation	Yes/No
Osteomyelitis	Yes/No
Gangrene	Yes/No
Nephropathy	Yes/No
HF at baseline	Yes/No
Smoking status	current smoker ex-smoker never smoked

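### If the treatment hazard ratio differs between 1245.25 and the heart failure trials, the SAF-M1 interactions for heart failure and diabetes absorb part of that difference; label the first and read the second from SAF-M2

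*Protocol*

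**What the plan says.** Protocol Section 9.7.2.3 gives the subgroup Cox model for SAF-M1 and SAF-M2: "the following factors will be included in the model: study, treatment, <subgroup>, treatment-by-<subgroup> interaction". SAP Section 4.3.2.3 agrees: "the following factors will be included in the model: study, treatment, <subgroup>, treatment by <subgroup> interaction". Inference needs "14 patients with events in total over the 2 treatment groups for each subgroup category". Both documents plan subgroup analyses for the two pools only, not for single studies. HF at baseline and diabetes are both listed subgroup variables (Protocol Table 9.3.3: 2, SAP Table 4.3: 3).

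Eligibility matters here. For the two HF trials, Protocol Section 9.1 describes the population as "T2D and non-T2D, age ≥18 years, chronic HF", and Section 9.2.2.2 requires "Chronic HF NYHA class II to IV". Section 9.2.2.1 states: "Study 1245.25 included patients with type 2 diabetes mellitus and increased cardiovascular risk".

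A treatment-by-study term appears only in the separate overall heterogeneity model (Protocol Section 9.9; SAP Section 4.3, trial heterogeneity). Section 9.9 expects some heterogeneity between trials and uses the subgroup analyses to judge the effect of population differences.

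**The concern.** A study main effect adjusts the baseline hazard, not the treatment effect. The HR for patients without HF is estimated from 1245.25 alone, while the HR for patients with HF comes mostly from the two HF trials. For diabetes it is the reverse: the HR without diabetes comes from the HF trials alone, and the HR with diabetes comes largely from 1245.25. A difference in treatment HR between 1245.25 and the HF trials is then partly reported as an HF or diabetes interaction.

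At stake is how a SAF-M1 table row is read. A regulator could take an HF interaction on amputation as effect modification when it mainly contrasts trials. The event rule does not flag this, because it counts events over the pool and not where the within-trial contrast lies.

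**Working it through.** **1. Sizes (Protocol Section 9.5).** 1245.25: 2345 + 2342 = 4687 empagliflozin, 2333 placebo. 1245.110: 4126, taken as 2063 per arm. 1245.121: 2850, taken as 1425 per arm. Total 7020 + 4126 + 2850 = 13,996, which reproduces the protocol's approximate 14,000. The documents give no event count or error rate for the interactions.

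**2. Assumptions, not in the documents unless noted.**
- Follow-up: 2.6 years in 1245.25 (its median exposure, Protocol Section 9.1); 2 years (range 1.5-3) in the HF trials.
- HF share of 1245.25: 10% (5-20). Diabetes share of the HF trials: 50% (40-60).
- LLA per 100 patient-years: 0.65 in 1245.25; in the HF trials 0.6 (0.5-0.8) with diabetes and 0.15 (0.10-0.25) without.
- Treatment HR 1.0 in 1245.25 and 1.5 in both HF trials, with no subgroup interaction inside any trial.

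**3. Expected LLA events, and information v = e1·e0/(e1 + e0).**

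| Cell | Empagliflozin | Placebo | v |
|---|---|---|---|
| 1245.25, HF no | 71.29 | 35.48 | 23.69 |
| 1245.25, HF yes | 7.92 | 3.94 | 2.63 |
| 1245.110, all | 23.21 | 15.47 | 9.28 |
| 1245.121, all | 16.03 | 10.69 | 6.41 |
| 1245.25, all (T2DM) | 79.21 | 39.43 | 26.33 |
| 1245.110, diabetes | 18.57 | 12.38 | 7.43 |
| 1245.121, diabetes | 12.83 | 8.55 | 5.13 |

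Example: 4687 × 0.10 × 2.6 × 0.0065 = 7.92.

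**4. Share of the log-HR gap that enters the interaction.**
- HF: the HF-yes HR averages 1245.25 and the HF trials. Share ≈ (9.28 + 6.41)/(9.28 + 6.41 + 2.63) = 15.69/18.32 = 0.86. Fitting the four-term log-linear rate model to the expected counts gives 0.87, a spurious ratio of HRs of 1.42.
- Diabetes: the HR with diabetes is pulled towards 1245.25. Share ≈ 26.33/(26.33 + 7.43 + 5.13) = 0.68. The fitted value is 0.67, a ratio of 1.31 (no diabetes versus diabetes).
- With treatment-by-study added, both ratios are 1.00. With equal HRs in all trials the planned model also gives 1.00.

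**5. Range.** Over all 243 combinations of the values in step 2 the HF share is 0.62-0.97 and the diabetes share 0.45-0.80. If HF doubles the LLA rate within 1245.25, the central HF share is 0.76. Wider assumptions (2-30% HF in 1245.25; HF-trial rates 0.25 to 1 times the 1245.25 rate; rate ratios 1-2 for HF and 1-8 for diabetes) take HF down to 0.34 and diabetes up to 0.93. The low HF values need 20-30% HF in 1245.25 together with a low HF-trial event rate.

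**6. False-positive interactions at 5% (LLA, 4000 simulated runs).** HF: 5%, 8% and 20% at HF-trial HRs of 1.0, 1.25 and 1.5. By hand at 1.5: SE ≈ √(1/18.32 + 1/23.69) = 0.31; log 1.42/0.31 = 1.13, so about 20%. Diabetes stays near nominal (normal approximation 7.5% at 1.5). The overall heterogeneity test has 19% power at 1.5. A false HF interaction together with a non-significant heterogeneity test occurs in 3%, 4% and 7% of runs.

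**7. Precision within 1245.25 for HF.** SE = √(1/2.63 + 1/23.69) = 0.65. With 20% HF the v values are 5.26 and 21.06, giving 0.49; with 5% they are 1.32 and 25.01, giving 0.89. Expected events in HF patients are 7.92 + 3.94 ≈ 12, which reaches 14 in about 31% of runs.

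**8. AEs related to amputation (rates assumed five-fold, HR 1.0 versus 1.2).** Spurious ratio 1.17 for HF (19% false positives) and 1.14 for diabetes (7.5%). The within-1245.25 HF SE is 0.29.

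**The case against.** The strongest case is that this is a reporting matter which the plan largely covers. All analyses are exploratory. Two pools exist because the populations differ. Study-level results, HR forest plots and a treatment-by-study test will show trial differences, and sources of heterogeneity are to be discussed in the report. Using subgroups to explore population differences arguably tolerates a partly between-trial contrast. Much of this stands, and it is why the point is minor. Still, those displays neither correct nor label the SAF-M1 interaction, and no planned analysis gives a within-trial HF interaction.

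A second objection is that adding treatment-by-study throughout SAF-M1 would be wrong. It stands.
- Diabetes: with that term 1245.25, which has a single diabetes category, contributes nothing. The result is essentially the planned SAF-M2 one (SE 0.631 from both at HR 1.5).
- HF: the added term removes bias but loses more precision. Root mean squared error of the log interaction, planned versus with the term, is √(0.351² + 0.312²) = 0.47 versus 0.65 at HR 1.5, and 0.37 versus 0.65 at HR 1.25.
- LLA without diabetes: expected events are 5.232 × (1 + HR), that is 10.5, 11.8 and 13.1 at HRs of 1.0, 1.25 and 1.5. All are below 14, so the test would often not be run.

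Three stronger readings are tempting but unsupported. A reader might infer that the SAF-M1 interactions are biased as planned; they are not if the trials share one HR, and the documents give no gap. A reader might infer that the weaker capture of amputations in 1245.25 is enough to create an interaction; under-capture equal in both arms is absorbed by the study term (ratio 1.00 at 50-90% capture). A reader might also expect frequent false HF findings. A rate of 37-38% does appear with a gap of 1.97, but that figure is the canagliflozin-versus-placebo HR in Protocol Section 7, not a difference between these trials, and it rests on 60 replicates per scenario.

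**Conclusion.** The concern holds in conditional form. The structure follows from the documents: there is no treatment-by-study term, and one category of each variable is confined to one side of the trial split. The size rests on proportions and rates that the documents do not give. The HF interaction takes most of any HR gap when HF is about 10% or less of 1245.25 (0.76-0.87 centrally, 0.34-0.97 over wider assumptions). The diabetes interaction takes about two thirds (0.45-0.93). The gap that matters is between 1245.25 and the HF trials; a gap between the two HF trials alone creates no HF contrast. Because the work is exploratory, the consequence is misinterpretation, not loss of a controlled error rate. This is a minor point with a cheap improvement.

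**What to change.** For LLA and for AEs related to amputation, amend SAP Section 4.3.2.3 and Protocol Section 9.7.2.3 as follows.

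1. **Diabetes.** Take the interaction estimate, confidence interval and p-value from the already planned SAF-M2 model. Do not report the SAF-M1 diabetes interaction as effect modification. No extra SAF-M1 model is needed.
2. **HF at baseline.** Keep the planned SAF-M1 model, with a footnote that its interaction is largely a contrast between 1245.25 and the HF trials. Beside it, report the treatment-by-HF interaction and the HF yes/no HRs within 1245.25. Apply the 14-event rule to the 1245.25 HF categories, and describe only if it is not met.

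The cost is some wording, a footnote and one extra model per outcome; no planned analysis is removed. The within-trial HF estimate will be imprecise. For LLA the SE of the log interaction is about 0.5-0.65 with 10-20% HF in 1245.25 and larger with fewer, so it will often be descriptive only. For AEs related to amputation it is about 0.29 under the assumed five-fold rates.
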